ID: 2021-135

Date: 1, October, 2021

The Effectiveness of Augmented Dyadic Interventions to Boost Quality of Life Among Stroke Survivors and Preparedness of Care Partners in Pakistan.

Title:

The Effectiveness of Augmented Dyadic Interventions to Boost Quality of Life Among Stroke Survivors and Preparedness of Care Partners in Pakistan.

The Effectiveness of Augmented Dyadic Interventions to Boost Quality of Life Among Stroke Survivors and Preparedness of Care Partners in Pakistan.

Project Summary

Study Background

Stroke is a leading cause of mortality and disability worldwide, resulting in significant physical deficits and psychological problems for survivors and their families. The impact of stroke can be devastating, affecting not only the individual but also their loved ones.

Study Objective

- 1) The objective of the study is to evaluate the efficacy of skill building dyadic intervention in improving dyad (care partner based) quality of life after stroke by focusing on the quality of life and outcomes of the stroke survivors and their care partners living at home post stroke occurrence.

- 2) To assess and evaluate the effect of outcomes on quality of life of dyad members and reducing caregiver burden among stroke survivors and their care partners by using a dyadic intervention.

The Effectiveness of Augmented Dyadic Interventions to Boost Quality of Life Among Stroke Survivors and Preparedness of Care Partners in Pakistan.

Study Design

This study is classified as an interventional study, with the primary purpose of prevention. The study phase is not applicable (N/A). The interventional study model is a parallel assignment, where participants will be randomly assigned to either the experimental group or the control group. The study will employ single masking, where only the participant will be blinded to the group assignment.

The interventional study design is single-blind, randomized controlled trials with repeated measures. Each group will include 196 subjects (98 stroke survivor + 98 care partner). Total no. of individuals will be 392 which have 196 stroke survivor and 196 care partners. Out of 196 pairs the 98 pairs will be kept control. After baseline assessment, the responsible assessor will be telephoned with patients identification details obtained from hospital, rehabilitation centers of Pakistan. Permission from the patients or caregivers will be taken on consent form before the start of the assessment.

Randomization

Participants will be randomly assigned to either the experimental group or the control group. This randomization will ensure that the groups are comparable in terms of demographic characteristics, reducing the risk of bias and increasing the validity of the results.

Study Population

The Effectiveness of Augmented Dyadic Interventions to Boost Quality of Life Among Stroke Survivors and Preparedness of Care Partners in Pakistan.

This study will be conducted upon stroke survivors and their care partner after discharge from the hospital. A care partner is defined as the main person (Spouse, Mother, Father, Sister, Brother, Son and Daughter) helping with activities of daily living and advocating on behalf of the stroke survivors. A consent form will be obtained from targeted stroke survivors and care partners.

A total of 392 participants, comprising 196 stroke survivors and 196 care partners, will be recruited voluntarily from a tertiary care hospital. The participants will be selected based on specific inclusion and exclusion criteria.

Inclusion Criteria

To be eligible for participation, stroke survivors must meet specific criteria. They must be aged 18-75 years, have a confirmed diagnosis of stroke and be discharged from the hospital. Additionally, they must participate voluntarily, be able to speak Urdu, and have no significant physical or psychological disability. Furthermore, care partners must be identified as primary care partners.

Exclusion Criteria

Participants will be excluded from the study if they meet certain criteria. These include acute illness, preexisting diseases before stroke, life expectancy of 6 months or less, global aphasia, and dementia on the Mini-Mental State Examination (score <22). Additionally, participants with a

The Effectiveness of Augmented Dyadic Interventions to Boost Quality of Life Among Stroke Survivors and Preparedness of Care Partners in Pakistan.

history of ongoing psychoactive substance abuse or terminal illnesses like renal failure or end-stage cancer will be excluded.

Intervention

Participants will be randomly assigned to either the experimental group or the control group. The experimental group will receive a five-session intervention, consisting of three face-to-face sessions and two telephonic sessions. In contrast, the control group will receive routine care. A five-session intervention will be delivered by trained nurses. The intervention aims to provide education, support, skills and guidance to stroke survivors and their care partners

Table 1: Nurse led Augmented dyadic interventions contents

Session	Key Content
Session 1 (Two weeks later of discharge)	Introduction to stroke and different aspects of management: The information on stroke, stroke consequences, prevention, and management aspects. Also to enhance the family dyad understanding regarding stroke and its effects. Duration: 60 mins, Mode: Face to face, Format discussion
Session 2 (three weeks later of discharge)	Promotion of care and demonstration of self-care activities: Instructions on the management of pressure areas and prevention of bedsores, dressing and how to keep personal hygiene, continence, physical activity, nutrition, positioning, facilitating transfers, daily living tasks and gait facilitation. It also include the hands-on training on lifting and handling techniques, facilitation of mobility and transfers, continence, assistance with personal activities of daily living and communication, tailored to the needs of individual patients.

ID: 2021-135

Date: 1, October, 2021

The Effectiveness of Augmented Dyadic Interventions to Boost Quality of Life Among Stroke Survivors and Preparedness of Care Partners in Pakistan.

Duration: 60 mins, Mode: Face to face, Format: Demonstration and skill development

Data Collection:

Data will be collected at multiple time points. Pre-test data will be collected at baseline, followed by post-test data at 3, 6, and 12 months after the intervention. Structured interviews and self-report questionnaires will be used to collect data.

Outcome Measures:

The study will assess two primary outcomes. For stroke survivors, quality of life will be measured using a stroke-specific quality of life questionnaire. For caregivers, burden will be assessed using the Zarit Burden Interview.

Statistical Analysis Plan (SAP):

The Effectiveness of Augmented Dyadic Interventions to Boost Quality of Life Among Stroke Survivors and Preparedness of Care Partners in Pakistan.

The Statistical Analysis Plan (SAP) outlines the statistical methods and procedures that will be used to analyze the data collected in this study. SPSS 22 will be used for data analysis.

Descriptive statistics will be used to summarize the data, including frequency and percentage for categorical variables, and mean and standard deviation for continuous variables. This will provide an overview of the characteristics of the study sample and the distribution of the variables.

Inferential statistics will be used to examine the relationships between variables.. Specifically, independent t-tests will be used to compare means between two independent groups (e.g., experimental vs. control group), paired t-tests will be used to compare means between two related groups (e.g., pre-test vs. post-test scores), and Pearson correlations will be used to examine the relationship between two continuous variables.

Data will be collected at four time points: baseline (pre-test), 3 months after the intervention, 6 months after the intervention, and 12 months after the intervention. This will allow us to examine the changes in the outcome variables over time and assess the effectiveness of the intervention.

The data analysis procedure will involve several steps. First, the data will be cleaned and checked for missing values. Then, descriptive statistics will be used to summarize the data. Next, inferential statistics will be used to examine the relationships between variables and test hypotheses. Finally, the results will be interpreted and conclusions will be drawn. By following this SAP, we aim to

ID: 2021-135

Date: 1, October, 2021

The Effectiveness of Augmented Dyadic Interventions to Boost Quality of Life Among Stroke Survivors and Preparedness of Care Partners in Pakistan.

ensure that the data analysis is conducted in a systematic and rigorous manner and that the results are reliable and generalizable.

郑州大学护理与健康学院

School of Nursing and Health Zhengzhou University

ETHICAL CONSIDERATIONS

Zhengzhou University Henan China

TITLE: Augmented dyadic interventions to boost quality of life among stroke survivors and their care partners in Pakistan.

I undertake that:

I will abide by the declaration of World Medical Association (WMA) make at Helsinki (2008) regarding the ethical principles for medical research involving human subjects.

1. The Health of the subject will be the prior consideration.

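### The masking rule leaves the outcome assessor unmasked, although some data are collected by interview, both primary outcomes are subjective, and the mode of administration of each is not stated

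*Combined protocol and SAP*

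**What the plan says.** The Study Design section sets the masking rule: "The study will employ single masking, where only the participant will be blinded to the group assignment". It then labels the trial accordingly: "The interventional study design is single-blind, randomized controlled trials with repeated measures". The same section shows that an assessor role exists: "After baseline assessment, the responsible assessor will be telephoned with patients identification details obtained from hospital, rehabilitation centers of Pakistan". It does not say whether that person is masked, or whether the call conveys allocation.

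The Data Collection section gives two modes of collection: "Structured interviews and self-report questionnaires will be used to collect data". It does not tie either mode to an outcome. The Outcome Measures section names one primary outcome for each member of the dyad: "For stroke survivors, quality of life will be measured using a stroke-specific quality of life questionnaire" and "For caregivers, burden will be assessed using the Zarit Burden Interview".

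The Intervention section describes the contrast: "The experimental group will receive a five-session intervention, consisting of three face-to-face sessions and two telephonic sessions" and "In contrast, the control group will receive routine care". Trained nurses deliver the sessions. The documents do not say whether those nurses may also collect outcomes.

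**The concern.** Because the rule confines masking to the participant, the assessor falls outside it by instruction, not by omission. Quality of life and caregiver burden are graded, subjective reports. When such items are put by an interviewer, the way they are read, explained, prompted or recorded can move the score. An interviewer who knows the arm could do this differently in the two groups at each of the three follow-up visits.

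The text also permits a less visible route. A nurse who ran a dyad's sessions could later collect that dyad's outcomes, while control dyads have had no sessions and so no delivering nurse. Any tendency to give agreeable answers to a familiar nurse would then act in the experimental arm only, and its likely direction would favour the intervention. The planned t-tests and correlations could not separate such a shift from a treatment effect.

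**Working it through.** **Step 1. Who is masked.** Study Design masks participants only. The sections on randomisation, intervention, data collection and outcome measures, and the SAP, add no masking of assessors. So the assessor is unmasked under the plan's own rule.

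**Step 2. Whether an assessor can affect the primary outcomes.** Three facts have to be read together:

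- Data Collection uses both interviews and self-report questionnaires, so staff elicit at least some of the data.
- The survivor outcome is called a questionnaire, with no mode stated.
- The caregiver outcome has the word interview in its title, but that is the name of the instrument, not a statement of how it will be given.

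Interview administration of either primary outcome, or of both, is therefore permitted but not established.

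**Step 3. Whether deliverer and assessor are separated.** Study Design speaks of an assessor and Intervention speaks of trained nurses. The different role names are compatible with different people, but no sentence requires it.

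**Step 4. Illustration of size.** The plan gives no figure for assessor bias to reproduce. The inputs are:

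- n = 98 dyads per arm (Study Design). The sample arithmetic is consistent: 98 + 98 = 196 individuals per group, and 2 × 196 = 392 in total.
- An independent t-test between groups (SAP).
- Assumed, because the documents are silent: two-sided α = 0.05, all 98 per arm analysed, one test, no true effect.
- Assumed: an arm-dependent shift b, in SD units, of 0, 0.1, 0.2 or 0.3.

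The standard error of the difference in SD units is √(2/98) = 1/7 = 0.1429, so the noncentrality is b ÷ (1/7) = 7b. The degrees of freedom are 2 × 98 − 2 = 194, with critical value 1.972. The rejection probability is P(T > 1.972) + P(T < −1.972), where T is noncentral t with 194 degrees of freedom and noncentrality 7b. The normal approximation is Φ(7b − 1.96) + Φ(−7b − 1.96).

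| Assumed shift b (SD) | Noncentrality 7b | Noncentral t | Normal approximation |
|---|---|---|---|
| 0 | 0 | 0.050 | 0.050 |
| 0.1 | 0.7 | 0.107 | 0.108 |
| 0.2 | 1.4 | 0.286 | 0.288 |
| 0.3 | 2.1 | 0.552 | 0.556 |

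The false-positive chance is thus about 5%, 11%, 29% or 55%. The zero row belongs in the range: it is roughly where a wholly self-completed outcome would sit as regards the interviewer's contribution.

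**The case against.** The strongest reply is that the plan may not rely on interviewers for its primary outcomes at all. If both instruments are self-completed, the participant is in effect the assessor, the interviewer's shift is close to zero, and masking staff gains little. Participants who know they had five sessions or routine care could still colour their answers before a fully masked interviewer. The arithmetic above is also generic: it holds for any arm-dependent shift, including participants' own reporting bias, so it does not show that the interviewer is the source.

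All of this stands as a limit on the size and certainty of the concern. It does not remove it. Interviews are planned, the mode for each primary outcome is left open, and the masking rule as written allows unmasked interviewing for both.

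Four stronger readings are tempting, and the documents do not support them:

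- **That both primary outcomes are collected by structured interview.** Neither outcome is given a mode.
- **That the interviewer is the only person who could be kept blind.** The documents do not discuss feasibility, and an analyst could be masked too.
- **That the telephone call discloses the arm.** The sentence mentions identification details and says nothing of allocation. It is no evidence of a leak, although it gives no explicit safeguard either.
- **That bias in favour of the intervention is certain.** It depends on interview administration, on the assessor learning the arm, and on that knowledge affecting what is asked or recorded.

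**Conclusion.** The concern holds in a conditional form. The assessor is unmasked by the plan's own rule, some data are collected by interview, both primary outcomes are subjective, and neither the mode for each outcome nor the separation of assessor from deliverer is stated. Following the text therefore exposes the results to an avoidable risk of assessor bias.

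The size of that risk cannot be derived from the documents. The range of about 5% to 55% rests on an assumed shift of 0 to 0.3 SD, an assumed two-sided 5% level and complete data from 98 per arm. It shows how sensitive the comparison is, not what bias to expect. The point merits a change because the remedy is cheap, not because a large bias has been shown.

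**What to change.** In Study Design, change the masking sentence so that the assessors who collect outcomes at 3, 6 and 12 months are masked to group. Then add the following:

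- The telephone call to the assessor carries no allocation.
- A nurse who delivered sessions to a dyad does not collect that dyad's outcomes.
- Data Collection states, for each primary outcome, whether it is given by interview or self-completed.
- Dyads are asked at the start of each follow-up visit not to reveal what they received.
- The assessor records a guess of the arm at the end of the visit, so that the success of masking can be reported.

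The cost is protocol wording and a rostering constraint. The plan already names assessor and nurse roles separately, so extra staff are not clearly needed, but it gives no staffing numbers and this should be confirmed. Some dyads will reveal their arm anyway. Bias from participants who know their own arm is not removed by any of these changes, and the trial report should say so.

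### Two unranked primary outcomes at three visits, with no primary contrast, significance level, multiplicity rule or success rule, leave the deciding result open until the data are seen

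*Combined protocol and SAP*

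**What the plan says.** Under Outcome Measures: "The study will assess two primary outcomes". For survivors, "quality of life will be measured using a stroke-specific quality of life questionnaire"; for care partners, the outcome is the Zarit Burden Interview. Neither is placed above the other, and nothing says whether one or both must succeed.

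Under Data Collection, a baseline assessment is "followed by post-test data at 3, 6, and 12 months after the intervention". No visit is called primary. The SAP says of the set of time points: "This will allow us to examine the changes in the outcome variables over time and assess the effectiveness of the intervention".

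The SAP's only method for comparing the arms is this: "independent t-tests will be used to compare means between two independent groups (e.g., experimental vs. control group". Beside it stands a within-group method: "paired t-tests will be used to compare means between two related groups (e.g., pre-test vs. post-test scores". The SAP does not say whether the paired tests may support a claim of effectiveness. It assigns neither test to a particular outcome or visit.

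The analysis steps end: "Next, inferential statistics will be used to examine the relationships between variables and test hypotheses", and then "Finally, the results will be interpreted and conclusions will be drawn". No significance level, sidedness, adjustment, testing order or success criterion appears in the protocol or the SAP. Study Design describes repeated measures, but the SAP plans no repeated-measures model.

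**The concern.** A confirmatory trial needs to fix in advance which comparison decides it. Here the deciding outcome (two candidates) and the deciding visit (three candidates) are both open, and the paired pre/post tests offer a further route to a positive statement. An analyst could follow the plan to the letter and still choose, after seeing the results, which of them counts as the answer. The false-positive rate of the primary claim is then not controlled at any stated level, and a reader of the report could not tell a prespecified finding from a selected one.

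Reading the two outcomes as separate claims, one per member of the dyad, does not remove the problem. Each claim would still have three unranked visits.

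**Working it through.** **Inputs from the documents.** Two primary outcomes (Outcome Measures); three post-baseline visits (Data Collection); independent t-tests between arms (SAP); 98 dyads per arm (Study Design).

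**Inputs assumed, because the documents give none.** Two-sided 5% per test; correlation between visits 0 to 0.9; correlation between outcomes 0 to 0.5; one score per outcome. For power: a true effect of 0.40 SD, and 0%, 15% or 25% dropout.

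**The plan's own figure.** The 98 per arm comes without significance level, power, effect size, SD or dropout, so it cannot be reproduced.

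**Step 1: independent tests, closed form.**
- One outcome, three visits: 1 − 0.95³ = 0.143 in either direction; 1 − 0.975³ = 0.073 in favour.
- Two outcomes, one visit: 1 − 0.95² = 0.098 in either direction.
- Two outcomes × three visits = six tests: 1 − 0.95⁶ = 0.265 in either direction; 1 − 0.975⁶ = 0.141 in favour.

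**Step 2: correlated tests.** Simulation of six normal test statistics, 1,000,000 draws per setting, equal correlation between visits, cross-outcome cross-visit correlation equal to the product of the two. There is no true effect except in the last row but one.

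| Rule (not stated in the plan) | Either direction | In favour |
|---|---|---|
| One outcome, any of three visits | 0.083–0.143 | 0.042–0.074 |
| Two outcomes, one visit, unadjusted | 0.091–0.098 | – |
| Any of six, visit correlation 0.5–0.8 | 0.173–0.235 | 0.087–0.122 |
| Any of six, visit correlation 0–0.9 | 0.148–0.265 | 0.074–0.141 |
| Both must win, each at any visit, no effect on either | – | 0.0018–0.0162 |
| Both must win, each at any visit, one truly improved by 0.40 SD (98 per arm) | – | 0.036–0.073 |
| One contrast per outcome, Holm | 0.046–0.050 | 0.023–0.025 |

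A single prespecified test gives 0.05 in either direction and 0.025 in favour. The both-must-win row with no effect can be checked by hand when the outcomes are uncorrelated: 0.073² = 0.0053 at visit correlation 0, and 0.042² = 0.0018 at 0.9. When one outcome truly improves, its own test is nearly always passed at some visit. What remains is the other outcome's chance of a false positive at any of three visits, which is why that row rises to about 7%.

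Simulated t-test data with 98 per arm (40,000 trials) gave 0.232 in either direction and 0.119 in favour for any of six, at visit correlation 0.5 and outcome correlation 0.3. The normal-statistic simulation gave 0.230 and 0.116 for the same setting.

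**Step 3: power cost of a rule, single visit.** The normal approximation to the detectable difference at 80% power is (z for alpha + 0.842) × √(2/n). With n = 98 this is (1.960 + 0.842) × 0.1429 = 0.400 SD at 5%, and (2.241 + 0.842) × 0.1429 = 0.440 SD at 2.5%. The table uses the noncentral t.

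| Analysed per arm | Detectable SD, 5% | Detectable SD, 2.5% (Holm, first step) | Both significant at 0.40 SD | Holm, at least one at 0.40 SD |
|---|---|---|---|---|
| 98 | 0.402 | 0.443 | 63%–68% | 85%–91% |
| 83 | 0.437 | 0.482 | 53%–59% | 78%–86% |
| 73 | 0.467 | 0.515 | 45%–52% | 73%–81% |

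The last two columns span outcome correlations 0 to 0.5. Single-test power at 0.40 SD is 0.796, 0.726 and 0.670 in the three rows; with uncorrelated outcomes the chance that both are significant is the square, for example 0.796² = 0.63.

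**The case against.** The strongest reply is that the plan never says it will run six primary tests. Both t-tests are introduced as examples, and no test is tied to an outcome or a visit. The mention of changes over time, with a design described as repeated measures, could point to change scores or a trajectory comparison. This stands. A reader might infer that the plan commits to six unadjusted tests with a false-positive rate of up to 26%. The documents do not support that: the count of six is an inference, the rule that any one suffices is stated nowhere, and 26% requires independence between visits, which is implausible for repeated scores on the same people. It is a bound, not an expectation.

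A second reply is that the outcomes belong to different people and may be meant as separate claims, or that both may have to succeed. Either is possible, and the inflation is then smaller. With both required and no effect on either, the rate is below that of a single test. But the plan states neither rule, and each leaves the visit open: 8%–14% in either direction per separate claim, or up to about 7% in favour, against 2.5%, when only one outcome truly improves.

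A third reply is that a single primary visit is not the only remedy. That is right. A reader might infer that one visit must be named, but one prespecified longitudinal contrast per outcome controls the error as well and suits the stated design.

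Missing text is a weak reply. Some content was absent from the text available, but the SAP prose reads continuously from its opening to its closing aim and contains none of these items.

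**Conclusion.** The concern holds as an omission with consequences: the plan fixes no primary contrast, significance level, multiplicity adjustment or success rule, so the deciding result can be picked after the data are seen. That the error rate is uncontrolled follows from the documents. Its size does not, because it depends on the unstated rule and on the assumed 5% level and correlations. The figure least dependent on how the outcomes are meant to combine is about 8%–14% in either direction (4%–7% in favour) for one outcome at three visits. The 17%–24% (9%–12% in favour) for any of six applies only if the plan is read as six tests with any one sufficient, at visit correlations of 0.5 to 0.8. This should be settled before any outcome data are seen.

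**What to change.** Before any outcome data are seen, amend the SAP to:

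1. Name one primary between-arm contrast per outcome, of the same kind for both: either one visit, or one overall arm contrast from a repeated-measures model.
2. Make all other visits and the paired pre/post t-tests secondary, and state that they do not support the effectiveness claim.
3. State the significance level and one of three rules: Holm across the two outcomes at an overall two-sided 5%; both outcomes significant at two-sided 5%, with no further adjustment; or two separate claims, each at 5% on its own single contrast.

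The cost is SAP text plus some power. With a single visit and Holm's first step, the detectable difference rises by about a tenth at each sample size considered (0.443/0.402 = 1.10 with 98 analysed per arm). Requiring both outcomes gives about 63%–68% power at an assumed 0.40 SD on each with 98 per arm, and less with attrition. Attrition may differ between survivors and care partners and will depend on the visit chosen, so that choice affects power though not the error rate. The plan states no power target, so the sponsor must judge which cost is acceptable. The power of a longitudinal contrast was not worked out here and should be calculated if that option is taken.

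### The SAP specifies no baseline-adjusted or longitudinal between-arm contrast, and lists pre/post paired t-tests, which have no control comparison, as inferential tests

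*Combined protocol and SAP*

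**What the plan says.** The Study Design section describes the trial as "single-blind, randomized controlled trials with repeated measures". It states that "Each group will include 196 subjects (98 stroke survivor + 98 care partner"), which is 98 dyads per arm. The Data Collection section gives the schedule: "Pre-test data will be collected at baseline, followed by post-test data at 3, 6, and 12 months after the intervention". There are two primary outcomes, survivor stroke-specific quality of life and care partner burden on the Zarit interview.

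The SAP names three inferential methods. For the first two it says that "independent t-tests will be used to compare means between two independent groups (e.g., experimental vs. control group), paired t-tests will be used" for related measurements, with pre-test and post-test scores as the example. The third is Pearson correlation. Of the four assessment times it says: "This will allow us to examine the changes in the outcome variables over time and assess the effectiveness of the intervention". In its list of analysis steps, "inferential statistics will be used to examine the relationships between variables and test hypotheses".

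The SAP mentions no baseline covariate, ANCOVA, mixed model, repeated-measures ANOVA or arm-by-visit term. It does not say whether the independent t-test is run on follow-up scores or on changes, at which visit it is run, or which of the listed tests decides effectiveness.

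**The concern.** The design collects what an efficient between-arm analysis needs, namely a baseline score and three follow-up scores on each person, but no listed method uses them together to compare the arms. Two separate problems follow.

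1. **Precision.** Recovery common to both arms cancels in the independent t-test, so that test is not biased. If it is run on follow-up scores, it discards the baseline. If it is run on change scores, it gains precision over follow-up scores only when baseline and follow-up correlate above 0.5, and loses precision below that.
2. **Interpretation.** The only listed test shown using pre-test and post-test scores together is the paired t-test, which looks within one group. Survivors enter after hospital discharge and are followed to 12 months after the intervention, so change under routine care is plausible, though the documents do not quantify it. An investigator could follow the SAP to the letter and report a significant pre/post change as effectiveness, when the same change occurred in the control arm.

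**Working it through.** **Inputs from the documents.** 98 survivors and 98 care partners per arm. The stated totals close: 98 + 98 = 196 per arm, and 2 × 196 = 392 individuals. Each primary outcome is measured on one member of the dyad, so each comparison has n = 98 per arm.

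**Inputs assumed, because the supplied text gives none.** Two-sided 5% level; 80% power for the detectable difference; baseline-to-follow-up correlation r from 0.3 to 0.7; equal SDs at baseline and follow-up, set to 1; an illustrative effect of 0.35 SD; no dropout, then 20% dropout (0.8 × 98 = 78.4, taken as 78 per arm).

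**Precision.** The between-arm difference has variance 2f/n, where f = 1 for follow-up scores, f = 2(1 − r) for change scores and f = 1 − r² for ANCOVA. Power comes from the noncentral t with noncentrality d × √(n / 2f), on 2n − 2 degrees of freedom (2n − 3 for ANCOVA). For d = 0.35, n = 98 and f = 1 the noncentrality is 0.35 × √49 = 2.45, which gives power 68%. At r = 0.5, ANCOVA has f = 0.75 and noncentrality 2.45 / √0.75 = 2.83, which gives power 80%.

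| Analysis | r | f | Detectable at 80% power (SD) | Power at 0.35 SD |
|---|---|---|---|---|
| t-test, follow-up score | any | 1.00 | 0.402 | 68% |
| t-test, change score | 0.3 | 1.40 | 0.476 | 54% |
| t-test, change score | 0.5 | 1.00 | 0.402 | 68% |
| t-test, change score | 0.7 | 0.60 | 0.312 | 88% |
| ANCOVA | 0.3 | 0.91 | 0.384 | 72% |
| ANCOVA | 0.5 | 0.75 | 0.348 | 80% |
| ANCOVA | 0.7 | 0.51 | 0.287 | 93% |

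ANCOVA does better than both t-tests at every r shown. With 78 per arm, power at 0.35 SD is 58% for the t-test on follow-up scores and 62% to 86% for ANCOVA.

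**Interpretation.** Suppose there is no treatment effect and both arms gain the same amount g (in SD). The paired t-test in one arm has noncentrality g × √98 / √(2(1 − r)) on 97 degrees of freedom. For g = 0.2 and r = 0.5 this is 0.2 × 9.90 / 1 = 1.98, so the probability p of significance is 50%. The arms are independent, so the experimental arm is significant and the control arm is not with probability p(1 − p); here 0.50 × 0.50 = 25%.

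| Shared gain (SD), r = 0.5 | Experimental-arm paired test significant | Experimental significant, control not |
|---|---|---|
| 0 | 5% | 5% |
| 0.1 | 17% | 14% |
| 0.2 | 50% | 25% |
| 0.3 | 84% | 14% |
| 0.5 | over 99% | 0.2% |

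At a gain of 0.2 SD, the experimental-arm test is significant in 38%, 50% and 72% of trials at r = 0.3, 0.5 and 0.7. The discordant pattern occurs in 24%, 25% and 20%.

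In simulated null trials (20,000 per setting, r = 0.3, 0.5 and 0.7, gains 0 to 0.5 SD), the independent t-test on follow-up scores and ANCOVA each rejected in 4.8% to 5.2%. The between-arm tests are therefore unaffected by a shared gain.

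**The case against.** The SAP does specify a between-arm test, names it first and gives experimental against control as its example. That test controls type I error in a randomised trial, so adding baseline adjustment improves the plan and corrects no error. At r = 0.3 the gain is small (0.40 to 0.38 SD; 68% to 72% power), and the 93% figure needs r = 0.7, which no document supports. Nor does the SAP say that paired tests decide effectiveness: its effectiveness sentence is about collecting data at four times. The paired-test percentages depend on assumed gains, and they apply only if the authors disregard their own between-arm test. The rates are also two-sided, so at zero gain half of the 5% is significant worsening. Finally, the precision figures are for single-visit ANCOVA, and the power of a mixed model was not computed.

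Most of this is fair and limits what can be claimed. The precision point is efficiency only. The paired-test rates show a mechanism and do not size the risk in this trial. Statements of absence cover only the supplied text, although the SAP section reads as continuous. Two things remain. The between-arm t-test has no stated scale, and that choice alone moves power between 54% and 88% in the cases above. The paired tests stand beside it unranked, among the methods meant to test hypotheses.

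**Conclusion.** The concern holds. For a randomised repeated-measures trial, the SAP gives no baseline-adjusted or longitudinal between-arm contrast and does not confine the paired tests to description. It should be corrected, but the plan is not invalid, because the independent t-test remains a sound comparison.

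- **Precision:** adjustment lowers the detectable difference from 0.40 SD to between 0.38 and 0.29 SD. This assumes r from 0.3 to 0.7, 98 per arm, two-sided 5%, 80% power and complete data.
- **Interpretation:** the risk is ambiguity about which result counts as effectiveness. Under an assumed shared gain of 0.2 SD and no treatment effect, relying on the experimental-arm paired test would give a false claim in 38% to 72% of trials over the same range of r, against about 5% for a between-arm test.

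**What to change.** For each primary outcome (survivor quality of life; Zarit burden), name one visit and make a single between-arm contrast at that visit the decisive analysis, with people analysed by randomised arm. Take it from a mixed model for repeated measures with arm, visit, arm-by-visit and baseline score, which also uses people who miss a visit. ANCOVA at the named visit with baseline as covariate is a simpler alternative. It gives the precision gain calculated above but, like the t-test, drops anyone missing that visit. Report the adjusted difference with its 95% confidence interval. Label the paired t-tests descriptive and state that they are not evidence of effectiveness.

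The cost is SAP wording and a little more analysis work. No new data and no new patients are needed.
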